## 6.4 Patient Inclusion

The study Performance Goals (PGs) are based on literature review (see ABRE CIP v1.4 Appendix A Scientific Literature Search). The distribution of patients in literature on which our PGs are based are:

- Acute Deep Vein Thrombosis (aDVT) – 26%
- Nonthrombotic iliac vein lesion (NIVL) – 30%
- Postthrombotic syndrome (PTS) – 44%
- 

During the course of the study, Medtronic may limit enrollments to specific indications (i.e. aDVT, PTS, or NIVL), if needed in order to achieve a distribution that is similar to the literature review used to develop the study PGs.

During the course of the study, Medtronic will constantly monitor the enrollment of patients in each category and, once the maximum number of patients included in a category is reached, Medtronic will inform the sites to stop the inclusion of those patients. The pre-defined maximum number of included subjects in each category is:

- aDVT: 31% = 62 included subjects
- NIVL: 35% = 70 included subjects
- PTS: 49% = 98 included subjects

## 7. Statistical Methods

---

### 7.1 Study Subjects

#### 7.1.1 Disposition of Subjects

The subject clinical follow-up compliance at each time will be provided at 30 days, 6, 12, 24 and 36 months via a flow diagram.

#### 7.1.2 Clinical Investigation Plan (CIP) Deviations

Protocol deviations will be reported descriptively by counts of type and listing by site.

#### 7.1.3 Analysis Sets

The primary analysis set will consist of all 'included' subjects who were enrolled and had the Abre system introduced into the vasculature. In general, all analyses will be performed using all evaluable subjects for primary effectiveness and safety analyses (evaluable subject definitions provided below). The point of enrollment for this study is once the subject has been consented and signed and dated the informed consent form. If the Abre system does not enter the vasculature, the subject is considered 'enrolled – not included' and will be followed for 30 days for safety assessment, but will not be included in the primary analysis set. In the case that the Abre stent entered the vasculature in a consented subject but the subject failed to have the study stent implanted, they will be followed for 30 days and exited from the study. These subjects will be considered 'included – not implanted' and will be part of the primary analysis set. The PMA primary analysis will occur when all 12-month follow-up data have been collected.

For the primary effectiveness endpoint, the primary analysis set will be 'included' subjects who are considered evaluable if:

- (a) the subject experiences at least one clinically-driven target lesion revascularization within 390 days; or
- (b) the subject has occlusion or restenosis  $\geq 50\%$  of the stented segment of the target lesion confirmed by core laboratory at 12 months visit; or
- (c) the subject has at least 330 days follow up without an event in the primary effectiveness endpoint.

For the primary safety endpoint, the primary analysis set will be 'included' subjects who are considered evaluable if:

- (a) the subject experiences at least one of the primary safety composite events within 30 days; or
- (b) stent-migration and stent thrombosis within 30 days are confirmed by imaging as assessed by core

laboratory; or (c) the subject has at least 23 days of clinical follow up without an event in the primary safety endpoint.

Secondary analyses for primary safety endpoint will be conducted on all implanted subjects in which the denominator for the primary safety endpoint will be the number of implanted subjects who had enough follow up (at least 23 days for 30-day follow-up visit) plus any subjects who had an event prior to the milestone visit.

Subject outcomes will be compared qualitatively to outcomes in patients with iliofemoral venous obstruction after medical management alone, based on historical data as reported in the literature.

## 7.2 General Methodology

Descriptive statistics of continuous characteristics/outcomes will be presented and include sample size, mean, median, standard deviation, minimum, and maximum. For categorical outcomes, the number and percentage of subjects in each category will be presented. Subject data listings and tabular and graphical presentations of results will be provided.

One-sided statistical tests will have p-values less than 0.025 deemed significant while two-sided tests will have p-values less than 0.05 deemed significant. Equivalent confidence intervals will also be utilized. Statistical analyses will be conducted in SAS version 9.4 or above (SAS Institute, Cary, N.C.) or another validated statistical software package.

Further details on data handling and analysis are found in Appendix A.

## 7.3 Center Pooling

Poolability of data across clinical study sites is justified on a clinical basis (i.e. all study sites use the same protocol) the sponsor monitors the site for protocol compliance, and the data gathering instruments are identical. The Food and Drug Administration also requires a statistical assessment of poolability. This is done by comparing the baseline characteristics across study sites. For categorical baseline variables such as gender, a generalized Fisher's exact test or equivalent test will be used and for quantitative variables, parametric or non-parametric analysis of variance (general linear models or an equivalent procedure) will be used.

The above statistical analyses do not result in an impediment to pooling, but rather assess the balance of baseline covariates across study sites. If any baseline covariate is found to be statistically significant by this process, multivariate analyses will be done to determine if the imbalance affected study outcome. This is done by using both the variable found out of balance and study site as possible covariates.

It may be necessary to combine two or more low enrolling study sites into pseudo-sites to allow these analyses. Sites with fewer than 6 subjects will be ranked by enrollment from low to high. Starting from the lowest enrollment site, sites will be combined into a pseudo site until the combined size reaches the median enrollment among all sites. This process will be repeated until all resulting sites have enrollment equal to or greater than 6 subjects. This will be done in a manner to preserve the structure of the study and prevent bias.

Because the ABRE Study is being conducted in the US and outside the US (OUS), an analysis will be undertaken to determine if the study sites within the US and OUS subsets are homogeneous in the baseline covariates. The statistical tests used will be the same as those discussed for site poolability.

Baseline characteristics to be considered as possible covariates are as following:

- Age
- Gender
- Race
- Ethnicity
- Chronic Obstructive Pulmonary Disease (COPD)
- Previous history of venous thromboembolism
- Venous Claudication
- Hyperlipidemia
- Known family history of DVT
- Pulmonary embolism
- Thrombophilia
- Peripheral Artery Disease (PAD)
- Hypertension
- Diabetes
- Smoking status
- Villalta score
- VCSS
- Venous disease category (aDVT vs. PTS vs. NIVL)

Poolability analysis will also be performed on the primary endpoints comparing across sites and geographical regions after adjusting for covariates difference. Logistic regression model will be utilized to include unbalanced covariates and site as an independent variable, and the study outcome as dependent variable to assess outcome difference. If the p-value of site effect is less than 0.10, further analyses will be undertaken to investigate the imbalance of the study outcome.

## 7.4 Handling of Missing, Unused, and Spurious Data and Dropouts

### 7.4.1 Multiple Imputation

For primary effectiveness endpoint, primary analysis will be performed using all evaluable data. Multiple imputation will be performed as sensitivity analysis to assess the robustness of the study data to the missing endpoints. For subjects not evaluable for primary effectiveness endpoint, the multiple imputation will be carried out using the logistic regression approach for a dichotomous outcome using PROC MI in SAS for subjects not experiencing the event and not having endpoint data for at least 330 days of follow up.

The following variables will be included in the multiple imputation model as covariates:

- Age
- Gender
- Race
- Ethnicity
- Diabetes
- Venous Disease category (aDVT vs. PTS vs. NIVL)
- Villalta score

- VCSS
- Reference Vessel Diameter
- Lesion length

If there are relatively few missing data points (<10%) for a given baseline variable, a simple gender-specific imputation using the mean (for continuous variables) or median (for dichotomous or categorical variables) of the non-missing values will be done. If there are >10% missing, the variable will be excluded from the imputation analysis. Five data sets will be imputed from these covariates and will mimic different realizations of the missing data. For the endpoint, the numerator (the numerator is the point estimate of the treatment for the effectiveness endpoint) and its relevant standard error (the pooled standard error of treatment for the effectiveness endpoint) will be pooled across the 5 data sets using established variance-adjustment methods (e.g., via PROC MIANALYZE in SAS) to create one overall numerator and denominator. The point estimate and the lower bound of the one-sided 97.5% pooled CI will be presented and compared to the primary analysis and the effectiveness PG

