### 10.12.6.2 Duplex Ultrasound (DUS)

The screening DUS was to be performed per standard of care in both limbs. All DUS after the index procedure were to be performed in the target limb, including an image of the contralateral CFV waveform.

The DUS exam immediately after the index procedure was to be performed between 0 and 7 calendar days from the index procedure. When the first exam after the procedure was non-diagnostic, a second exam was to be performed as soon as possible. Every effort should have been made to perform this within 7 calendar days after the index procedure. DUS was/will be performed to assess patency during the 6, 12, 24, 36 months follow-up visits.

All DUS examinations, except the screening DUS, should be performed according to the core laboratory guidelines and are analyzed by an independent core laboratory (See **Section 13.3**).

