#### 14.6 Handling of Dropouts and Missing Data

For those subjects not evaluable for primary effectiveness endpoint, multiple imputations will be carried out using the logistic regression approach for a dichotomous outcome using PROC MI in SAS for patients not experiencing the event and not having endpoint data for at least 330 days of follow-up.

The following variables will be included in the imputation model as covariates:

- Age
- Gender
- Race
- Ethnicity
- Diabetes
- Total occlusion
- Venous disease category
- Villalta score at baseline
- CEAP score at baseline
- VCSS class at baseline
- Reference vessel diameter
- Lesion length

If there are relatively few missing data points (e.g., <10%) for a given variable, a simple gender-specific imputation using the mean (for continuous variables) or median (for dichotomous or categorical variables) of the non-missing values will be done. If there are >10% missing data points, the variable will be excluded from the imputation analysis. Five data sets will be imputed from these covariates and will mimic different realizations of the missing data. For the endpoint, the numerator (the numerator is the point estimate of the treatment for the effectiveness endpoint) and its relevant standard error (the pooled standard error of

treatment for the effectiveness endpoint) will be pooled across the 5 data sets using established variance-adjustment methods (e.g., via PROC MIANALYZE in SAS) to create one overall numerator and denominator. The lower bound of the 97.5% pooled CI will be compared to the effectiveness PG.

The Tipping Point method will be adopted to further evaluate study primary objectives by assessing the impact of missing or unknown outcome data on study results. Tipping point analysis results for both primary effectiveness endpoint and primary safety endpoint will be reported.

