## 3. Introduction

The ABRE Study will evaluate the safety and effectiveness of the Abre™ venous self-expanding stent system (Abre stent) in patients with symptomatic iliofemoral venous outflow obstruction. The collected data will be used to support regulatory applications in seeking market approval for the stent in the United States and potentially other geographies, as well as presentations and publications.

The study is designed to meet Performance Goals (PGs) established via review of the clinical venous stent literature. The primary endpoints are as follows: a 30-day post-procedure Major Adverse Event PG of 12.5% for safety and a 12-month post-procedure Primary Patency PG of 75% for effectiveness.

A maximum of 200 implanted subjects from up to 35 sites worldwide are planned to be included in the study. Data from 160 subjects are needed to evaluate the primary effectiveness endpoint of primary patency at 12 months, and data from 193 subjects are needed to evaluate the primary safety endpoint of major adverse events at 30 days. A minimum of 40% of included subjects will be from the US. A maximum number of 40 subjects will be included per site (20% of the total study population).

The sample size includes correction for 20% lost-to-follow-up on the effectiveness endpoint and 3.5% lost-to-follow-up on the composite safety endpoint. The sample size is driven by the primary effectiveness and safety endpoints and based on a one-sided alpha of 0.025 and at least 80% overall study power.

A Premarket Approval application will be submitted to FDA when all available 12-month follow-up data have been collected.

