## 6.1 Performance Goal: Primary Effectiveness Endpoint

The primary effectiveness PG endpoint in this study is primary patency. The statistical hypothesis on this endpoint is that primary patency through 12 months will exceed a PG established from historical literature references using venous stenting as the treatment of choice. Formally, the null and alternative hypotheses to be tested appear below:

$$\begin{aligned}H_0: n &\leq PG \\H_A: n &> PG\end{aligned}$$

where  $n$  is the primary patency at 12 months in the study population and  $PG$  is the performance goal, which is calculated as follows. An extensive and independent review of the available literature produced references on venous stenting in similar patient populations. These data are derived from published studies of venous stenting which measured target vessel patency as an endpoint. To estimate the expected rate of primary patency in the study population at 12 months, the review of the available literature was used (see ABRE CIP Appendix A).

Based on the literature, the weighted mean expected primary patency was 85.7%. By subtracting a margin of indifference of 10% from expected performance ( $85.7\% - 10\% = 75.7\%$ ); consequently, the value of 75% is therefore taken as the  $PG$  for the current study. A margin of 10% has been commonly used for primary patency.

For analysis of the imaging component of primary patency, if a subject has both a valid venogram and DUS during the 12-month follow-up period then the venogram will be used. If no venogram is available, then the DUS will be used.

Further details regarding the analysis algorithm for primary patency are found in Appendix A.

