## 6.3 Sample Size Calculation

Primary Effectiveness: Using the assumptions above on the  $PG$  and anticipated outcome, we assume desired power of at least 92% under hypothesis testing relative to the performance goal at a one-sided alpha of 0.025. The resulting evaluable sample size required is then 160 subjects using exact binomial

test for a single proportion. Accounting for attrition during follow-up, the sample size is augmented by 20% to 200 subjects. Every effort will be made, however, to minimize loss to follow-up.

Primary Safety: Using the assumptions above on the performance goal and anticipated outcome, we assume desired power of at least 92% under hypothesis testing relative to the PG at a one-sided alpha of 0.025. The resulting evaluable sample size required is then 193 subjects using exact binomial test for a single proportion. Accounting for attrition during follow-up, the sample size is augmented by 3.5% to 200 subjects. Every effort will be made, however, to minimize loss to follow-up.

In summary, the overall power of the study is at least 84% while the effectiveness and safety PGs and the projected rates needed to achieve them are as follows:

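### The multiple-imputation sensitivity analysis for 12-month patency ignores the 30-day and 6-month core-laboratory duplex, so an untreated interim stent failure without a 12-month result is imputed from baseline profile alone

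*SAP*

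**What the plan says.** **Role of the imputation.** SAP 7.4.1 makes the evaluable-subject analysis primary and gives multiple imputation the role of a sensitivity analysis. It imputes subjects who have had no event and lack endpoint data through at least 330 days.

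**Covariates.** After "The following variables will be included in the multiple imputation model as covariates" the SAP lists age, gender, race, ethnicity, diabetes, venous disease category, Villalta, VCSS, reference vessel diameter and lesion length. Protocol 14.6 states that its scores are baseline scores. It also lists "Total occlusion" and baseline CEAP, which the SAP does not. Neither list contains post-procedure imaging.

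**Number of imputations.** "Five data sets will be imputed from these covariates"; the results are then pooled and the lower 97.5% limit is compared with the goal.

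**Interim imaging.** Protocol 10.7 and 10.8 schedule target-limb duplex at 30 days and 6 months. Protocol 10.12.6.2 says "DUS was/will be performed to assess patency during the 6, 12, 24, 36 months follow-up visits", and sends every duplex except the screening scan to the core laboratory.

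**Other missing-data analyses.** SAP 7.4.2 plans a tipping-point analysis for both primary endpoints. SAP 7.9.1.2 adds a supportive Kaplan-Meier analysis of patency.

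**The concern.** The imputation is there to show whether the 75% conclusion is robust to missing 12-month outcomes. The form of missingness that matters most is a subject whose stent has already narrowed or closed and who then leaves. The plan schedules the scan that would show this, but the imputation model does not use it. Conditional on baseline profile, the model treats dropout as unrelated to early stent status, which is the assumption a robustness check should be able to relax. The result could then look more reassuring than the collected data justify.

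Two smaller matters affect the same analysis. Five imputations leave visible run-to-run noise in the pooled limit when up to 20% of outcomes are missing. And the SAP and the current protocol disagree on the covariate list.

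**Working it through.** **1. Does such a subject reach the imputation model?** Take a subject with restenosis or occlusion at 6 months (visit window 150 to 210 days), no clinically driven revascularization, who leaves before day 330.

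- Evaluability rule (a), SAP 7.1.3, requires a clinically driven revascularization within 390 days: not met.
- Rule (b) requires occlusion or restenosis at the 12-month visit: not met.
- Rule (c) requires at least 330 days of follow-up: not met.
- SAP 10.3.2.2 does not carry an earlier imaging failure forward to a later visit.
- SAP Table 4 accepts unscheduled 12-month imaging only on days 271 to 420, so a 6-month scan cannot serve as the 12-month result.

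The primary analysis drops this subject, and the imputation draws the outcome from baseline and lesion variables.

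**2. The plan's own figures.** SAP 3 states "Data from 160 subjects are needed to evaluate the primary effectiveness endpoint of primary patency at 12 months", and SAP 6.3 states "we assume desired power of at least 92% under hypothesis testing relative to the performance goal at a one-sided alpha of 0.025". SAP 6.1 gives an expected rate of 85.7% and a goal of 75%. The exact binomial with n = 160 and rejection at 131 or more gives power 0.9288 at 0.857 and alpha 0.0247 at 0.75, as printed in the SAP. The threshold is 131/160 = 81.9%. Attrition: 160/0.80 = 200, so up to 40 outcomes may be missing.

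**3. Overstatement per affected subject.** Let k be the number affected and q their true probability of being patent at 12 months. Neither is in the documents; both are assumptions. With baseline covariates taken as uninformative, the model imputes patency at 0.857, so

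overstatement = k × (0.857 − q) / 200.

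| k | q = 0 | q = 0.2 | q = 0.5 |
|---|---|---|---|
| 1 | 0.43 points | 0.33 | 0.18 |
| 3 | 1.3 | 1.0 | 0.5 |
| 5 | 2.1 | 1.6 | 0.9 |
| 8 | 3.4 | 2.6 | 1.4 |

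**4. Effect on the imputation's lower limit.** Simulation: 160 evaluable, 40 missing, five imputations, Rubin's rules, mean lower 97.5% limit. The baseline-only model draws all 40 at the evaluable rate; the alternative draws k of them at patency q.

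| Evaluable result | Baseline-only limit | With interim status used |
|---|---|---|
| 137/160 (85.6%) | 79.9% | q = 0.02: k = 8, 76.4%; k = 12, 74.6%. q = 0.2: k = 12, 75.6%; k = 16, 74.1%. q = 0.5: k = 16, 76.5% |
| 134/160 (83.8%) | 77.8% | q = 0.02: k = 8, 74.4% |
| 131/160 (81.9%) | 75.7% | q = 0.02: k = 2, 74.8%. q = 0.2: k = 2, 75.0%; k = 4, 74.3%. q = 0.5: k = 4, 74.9% |

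**5. Five against 50 imputations.** Same set-up with the baseline-only model: the seed-to-seed standard deviation of the lower limit is about 1.0 point with five imputations and 0.27 with 50. At 131/160 about 22 to 24% of seeds put the five-imputation limit at or below 75%, against about 0.2% with 50. At 137/160 the number of imputations practically never changes the result.

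**The case against.** **The plan does not rest on this analysis.** Pass/fail uses evaluable subjects, and the tipping-point analysis varies the missing outcomes without assuming they are missing at random. This stands, and it bounds the harm. But as written the tipping-point analysis does not use the interim scans, so it cannot say which of its scenarios the collected data make likely. The Kaplan-Meier analysis does not say how interim imaging failures are counted or dated.

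**Not every early failure is imputed.** A reader might infer that anyone whose stent failed before dropout is treated as a success candidate. The documents do not support that: a clinically driven revascularization within 390 days counts as failure even without later imaging (SAP 10.3.2.2).

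**Imputed subjects are not given the overall average.** The model conditions on disease category and lesion variables, and the literature review's 12-month patency runs from 80.5% (post-thrombotic) to 94.8% (non-thrombotic) (Protocol Appendix A, Table XIII). The flat 0.857 above is a simplification.

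**Interim duplex is imperfect evidence.** Mandatory venographic confirmation applies only at 12 months (Protocol 10.12.6.1), and some lesions may be patent later. This is why q is varied.

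**Five imputations are efficient enough.** At 20% missing information the relative efficiency is 1/(1 + 0.2/5) = 96%. That is true of the variance of the estimate, but the limit near 75% still depends noticeably on the seed.

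**Sparse data.** About 0.143 × 160 = 23 failures are expected against ten covariates, some multi-level. A strong imaging predictor could cause separation. This is a fair point and is dealt with in the fix.

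**The covariate change is logged.** The SAP's version 3.0 history records an updated list, but gives no reason, and the later Protocol 2.0 still carries the longer list.

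A reader might also infer that the gender-specific mean or median fill-in would be applied to missing duplex results. SAP 7.4.1 confines it to baseline variables.

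**Conclusion.** The omission is real, and it affects a narrow group: interim core-laboratory restenosis or occlusion, no clinically driven revascularization within 390 days, and no 12-month result. For them the sensitivity analysis overstates pooled patency by up to about 0.4 points of 200 each, and by less if some are patent at 12 months. At the planned rate about 12 of 40 missing subjects would have to be affected to reverse the imputation result, and at q = 0.5 even 16 would not do so. At the 131/160 threshold about 2 to 4 are enough to bring it to the limit.

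These sizes rest on the full 40-subject attrition allowance, uninformative baseline covariates and assumed values of k and q. The documents give no count of affected subjects. A reader might infer that the trial's primary conclusion is biased by this or would be overturned. The documents do not support that, because the imputation does not enter the pass/fail test. One phrase leaves some doubt: restricting imputation to subjects without the event could be read as excluding a 6-month occlusion, but the 12-month-only imaging rules point the other way.

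**What to change.** In SAP 7.4.1:

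- Add the latest available core-laboratory duplex status before 12 months (patent, against at least 50% restenosis or occluded) as a predictor, with a penalised or simplified model if separation occurs. Alternatively, add a sensitivity analysis that counts interim imaging failures without a 12-month result as failures.
- Use at least 50 imputations.
- Reconcile the covariate list with Protocol 14.6 on total occlusion and CEAP, and state the reason for whichever list is kept.

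The cost is slightly more programming and possible sparse-data handling; the duplex scans are already scheduled and centrally read. Because the premarket application based on the 12-month data has already been submitted (Protocol Synopsis), the result would be reported as a supplementary re-analysis.

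### The multiple-imputation sensitivity analysis uses five imputations, no fixed seed and no stated pooling scale, so near the pass line its comparison with the 75% goal can change by seed alone.

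*SAP*

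**What the plan says.** SAP 7.4.1 separates two analyses. The main one is on observed outcomes: "For primary effectiveness endpoint, primary analysis will be performed using all evaluable data". Imputation comes second: "Multiple imputation will be performed as sensitivity analysis to assess the robustness of the study data to the missing endpoints".

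The imputation is logistic, in PROC MI, with ten listed covariates. On the number of imputations it says "Five data sets will be imputed from these covariates and will mimic different realizations of the missing data". The point estimate and its standard error "will be pooled across the 5 data sets using established variance-adjustment methods (e.g., via PROC MIANALYZE in SAS"), and the "lower bound of the one-sided 97.5% pooled CI will be presented and compared to the primary analysis and the effectiveness PG".

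Protocol 14.6 also plans five data sets and ends "The lower bound of the 97.5% pooled CI will be compared to the effectiveness PG". It does not call the analysis a sensitivity analysis.

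Neither document names a random seed, the scale on which the proportion is pooled, or the degrees-of-freedom rule. SAP 7.4.2 adds a tipping-point analysis for both primary endpoints, without detail.

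**The concern.** Two separate weaknesses affect the same reported number.

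1. **Monte Carlo noise.** With five imputations the between-imputation variance is estimated on 4 degrees of freedom. Both the pooled estimate and its standard error therefore depend visibly on the seed. When the observed result is close to the goal, one seed can put the lower bound above 75% and another below it. That is where a robustness check is most needed. With no seed fixed, the result also cannot be reproduced exactly, although SAP 8 requires double programming of all endpoints.

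2. **Scale of the limit.** Pooling a proportion and its standard error directly gives a Wald-type limit, which tends to be too high when the true rate is around 75%.

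At stake is how well the sensitivity analysis supports the primary result. The primary result itself is not at stake.

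**Working it through.** **Inputs from the documents.** 160 evaluable of 200, 20% attrition, goal 75%, expected patency 85.7% (SAP 6.1, 6.3); one-sided alpha 0.025 (SAP 7.2); five imputations (SAP 7.4.1).

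**Assumptions not in the documents.** Outcomes missing completely at random; Rubin's rules with Rubin's t degrees of freedom; raw-scale pooling unless stated. The base case is intercept-only imputation.

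**Step 1: reproduce the design.** For X ~ Bin(160, p), P(X ≥ 131) is 0.0247 at p = 0.75 and 0.9288 at p = 0.857, as in SAP 6.3. Also 160/(1 − 0.20) = 200, so up to 40 outcomes would be imputed.

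**Step 2: the pooled limit at 131/160 with 40 missing.**
- p = 131/160 = 0.81875
- Within-imputation variance: U = p(1 − p)/200 = 0.000742
- Between-imputation variance: B ≈ [40·p(1 − p) + 40²·p(1 − p)/160]/200² = (5.936 + 1.484)/40,000 = 0.0001855
- Total: T = U + (1 + 1/5)B = 0.000965, so √T = 0.0311
- r = 1.2B/U = 0.30; df = 4(1 + 1/0.30)² ≈ 75; t = 1.992
- Typical limit: 0.81875 − 1.992 × 0.0311 ≈ 75.7%

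The five-draw mean alone has seed SD √(B/5) = 0.6 point. Estimating B on 4 df raises the SD of the limit to about 1.0 point in simulation.

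**Step 3: seed dependence by simulation (raw scale, intercept-only, 131/160, 40 missing).**

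| Imputations | Seed SD of limit | Middle 95% of seeds | Seeds clearing 75% |
|---|---|---|---|
| 5 | 1.0 point | 73.4-77.3% | 77% |
| 20 | 0.4 point | 74.9-76.6% | 96% |
| 50 | 0.3 point | 75.3-76.4% | 99.8% |
| 100 | 0.2 point | 75.5-76.2% | >99.9% |

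Share of seeds clearing 75% with five imputations, by observed count: 128, 5%; 129, 23%; 130, 51%; 131, 77%; 132, 90%; 133, 97%; 137 (about the expected 85.7%), >99.9%. With fewer missing, the seed SD falls to 0.6 point (20 missing) and 0.4 point (10 missing).

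The chance that the count falls in 128-132, where roughly 5-95% of seeds pass, is 13% at a true rate of 85.7%, 38% at 81.9% (the SAP's required rate) and 7% at 75%.

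**Step 4: covariates.** I used 12 covariate terms unrelated to outcome and 60 simulated data sets per setting. Seed SD at five imputations stayed at 1.0 point. The share of data sets in which 5-95% of seeds pass was 98% at 131, 58% at 133 and 8% at 137. With 100 imputations the shares were 25%, 2% and 0%. A second run of the same size gave 100%, 48% and 0%, then 40%, 2% and 0%. These shares are rough, but the range of affected counts can be wider than without covariates.

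**Step 5: one-sided error at true patency 75%, n = 200.**

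| Imputation model | Raw, 5 imputations | Raw, more imputations | Logit |
|---|---|---|---|
| Intercept-only, 10-40 missing | 3.4-3.5% | 3.4% (100; 40 missing) | about 2.2% |
| SAP covariate list, 40 missing | 2.5-2.7% | 2.5-2.8% (50) | 1.5-1.7% |
| SAP covariate list, 10-20 missing | 3.1% | 3.1-3.2% (50) | 2.0-2.1% |

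The excess on the raw scale comes from the scale. The number of imputations hardly changes it.

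**The case against.** The strongest reply is that nothing is decided by this analysis. SAP 7.4.1 and 7.9.1.2 call it a sensitivity analysis. Effectiveness success is tied to the evaluable-data limit (SAP 7.9.1.2, protocol 14.4.1 and 14.5), and no alpha is assigned to the imputed bound. This stands. A reader might infer that the trial can pass or fail by seed, or that its one-sided error is about 3.5% instead of 2.5%. The documents support neither. The omission of the word sensitivity in protocol 14.6 does not create a success rule, and 3.5% is the top of a range that comes from a model without the SAP's covariates.

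Second, the instability is local. At 128-130 the exact test used for planning has already failed. At a true 85.7%, the chance that 131 or more are patent but the imputed bound fails by seed is only about 1.4-1.5%. This also stands for the size of the problem, but a robustness check that is stable only when the answer is clear gives little help near the goal.

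Third, a tipping-point analysis is planned as well. It is a separate safeguard, but it does not make the imputation result reproducible.

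Fourth, a reader might infer that the imputed limit is laxer than the primary one. The SAP names the exact binomial test for sample size but no interval method for effectiveness in 7.9.1.2, so that comparison is not established.

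Finally, the premarket application went in on 27 April 2020 (protocol synopsis), so a seed cannot now be pre-specified for that report. This affects how the fix is worded, not whether it is useful.

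**Conclusion.** The point holds as a limited improvement to a sensitivity analysis. With 40 of 200 missing and five imputations, the pooled lower bound has a seed SD of about 1 point. For about 129-132 of 160 patent under intercept-only imputation, and possibly a wider range with covariates, the comparison with 75% can change by seed alone. At the expected 85.7% it is essentially stable.

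Separately, raw-scale pooling gives a one-sided error of about 2.5-3.5% depending on the imputation model, against about 1.5-2.2% on the logit scale. Raising the number of imputations does not change this. Raw scale is an inference from the pooling description.

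All sizes rest on the assumed missing fraction, missingness mechanism, covariate effects and degrees-of-freedom rule. The primary test and the study success rule are unaffected.

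**What to change.** In SAP 7.4.1 and protocol 14.6:

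- Replace five with at least 100 imputations, and fix and document the seed.
- Pool the log-odds of patency, with variance 1/[n·q(1 − q)] in each completed data set, where q is its patent proportion. Back-transform the one-sided 97.5% lower limit before comparing it with 75%, and name the degrees-of-freedom rule.
- Have protocol 14.6 call this a sensitivity analysis, as the SAP does.

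If the 12-month analysis has already been run, rerun it this way and report the change with its reason, as SAP 7.12 requires.

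The cost is a few sentences, slightly more computing and a slightly less favourable limit. In my intercept-only check at 131/160 with 100 imputations, the limit moves from about 75.9% (raw) to about 75.1% (log-odds). No finite number of imputations removes seed dependence exactly on the line. In that check, with both changes, only the count 131 remained sensitive (about 73% of seeds clear 75%, against 0.1% at 130 and 100% at 132). The documented seed makes that case reproducible.
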